### **11.5. Device Accountability**

The investigational devices will be provided by the Sponsor to the clinical sites. This will occur only after the site has been initiated and all regulatory approvals as well as required documentation have been collected from the site.

The devices shall be securely maintained, controlled, and used only in this clinical study. Additionally, the study personnel must follow the instructions related to the storage of the devices as noted in the Instructions For Use (IFU). Device Accountability Logs will be provided to the sites and will be used to track subjects and device allocations during the study.

The sponsor shall keep records to document the physical location of all investigational devices from shipment of investigational devices to the investigating sites until return or disposal.

Records shall be kept at each study site to document the physical location and conditions of storage of all investigational devices. Sites must not dispose of any devices for any reason at the site unless instructed to do so by the Sponsor. Any device that is disposed of at the site must be recorded in the Device Accountability Log. The Principal Investigator must document the reasons for any discrepancy noted in device accountability.

The principal investigator or an authorized designee shall keep records documenting the receipt, use, return and disposal of the investigational devices, which shall include the following:

- Date of receipt
- Identification of each investigational device
- Expiry date, as applicable
- Date of use
- Subject identification
- Date on which the investigational device was returned/explanted from subject, if applicable
- Date of return of unused, expired, or malfunctioning investigational devices, if applicable

This accounting will be verified by the Sponsor or its designee during regular visits on site, and copy of the Device Accountability Logs will be made.

## **11.6. Data Handling and Record Keeping**

### **11.6.1. Data Collection, Processing and Review**

Subject data will be recorded in a limited access secure electronic data capture (EDC) system. The clinical database will reside on a production server hosted by [CRO] SAS. All changes made to the clinical data will be captured in an electronic audit trail and be available for review by the Sponsor or its representative. The software and database have been designed to meet regulatory compliance for deployment as part of a validated system compliant with laws and regulations applicable to the conduct of clinical studies pertaining to the use of electronic records and signatures. Database backups are performed regularly.

The Investigator provides his/her electronic signature on the appropriate eCRFs in compliance with local regulations.

Manual and/or automatic queries will be created in the EDC system and will be issued to the center for appropriate response. Site staff will be responsible for resolving all queries in the database.

### **11.6.2. Data Retention**

Sponsor and Investigator will maintain the clinical investigation documents for a minimal period of fifteen (15) years after the clinical investigation is completed, or longer depending on national requirements. They will take measures to prevent accidental or premature destruction of these documents and ensure these are filed in a secure place. Investigator or Sponsor may transfer custody of records to another person or party and document the transfer at the investigation site, or at the Sponsor's facility.

## **11.7. Monitoring**

Monitoring will be performed during the study according to the monitoring plan to assess continued compliance with the protocol and applicable regulations. In addition, the monitor verifies that study records are adequately maintained, that data are reported in a satisfactory manner with respect to timeliness, adequacy, and accuracy, and that the Investigator continues to have sufficient staff and facilities to conduct the study safely and effectively. The Investigator/institution guarantees direct access to original source documents by the Sponsor, their designees, and appropriate regulatory authorities.

The study site may also be subject to a quality assurance audit by the Sponsor or its designees, as well as inspection by appropriate regulatory authorities. It is important that the Investigator and relevant study personnel are available during on-site monitoring visits or audits and that sufficient time is devoted to the process.

## **11.8. Insurance**

Subjects who participate in this study will be insured against study related injury.

The Sponsor has obtained clinical trial insurance with appropriate coverage for the continuation of the entire study.

## **11.9. Suspension or Termination**

### **11.9.1. Premature Termination**

The Sponsor reserves the right to terminate the study at any stage but intends to exercise this right only for valid scientific or administrative reasons and reasons related to protection of subjects. Investigators, associated ECs, and regulatory authorities, as applicable, will be notified in writing in the event of study termination.

### **11.9.2. Criteria for Premature Termination of the Study**

Possible reasons for premature study termination include, but are not limited to, the following:

- Under the direction of AEMPS, after review of the safety data collected on the first five (5) patients through 30 days.
- The occurrence of unanticipated adverse device effects that present a significant or unreasonable risk to subjects enrolled in the study.
- An enrollment rate far below expectation that prejudices the conclusion of the study.
- A decision on the part of the Sponsor to suspend or discontinue development of the device.

### **11.9.3. Criteria for Suspending/Terminating a Study Site**

The Sponsor reserves the right to stop the inclusion of subjects at a study site at any time after the study initiation visit if no subjects have been enrolled or if the site has multiple or severe protocol violations/noncompliance without justification and/or fails to follow remedial actions.

In the event of termination of investigator participation, all study devices and testing equipment, as applicable, will be returned to the Sponsor unless this action would jeopardize the rights, safety or well-being of the subjects. The EC and regulatory authorities, as applicable, should be notified. All subjects enrolled in the study at the site will continue to be followed per this protocol. The Principal Investigator at the site must make provision for these follow-up visits unless the Sponsor notifies the investigational center otherwise.

## **11.10. Publication Policy**

Following completion of the study, the data may be considered for reporting at a scientific meeting or for publication in a scientific journal. In these cases, the Principal Investigator will be responsible for manuscript preparation and submission. The Sponsor shall be notified of any planned presentations or publications and shall have the opportunity to review any such materials. The Sponsor has final approval authority over all such issues.

Data, as well as any derivative works and intellectual property, arising from this clinical investigation are the exclusive property of the Sponsor. Data cannot be published without prior authorization from the Sponsor, but data and publication thereof will not be unduly withheld.

## APPENDIX 1 M-TRAP DEVICE EXPLANT PROCESSING PROTOCOL

Please follow this processing protocol after receiving a tissue specimen containing an M-Trap device.

1. Take high-resolution, clear photographs of the gross specimen. Please, establish the block identification key in a copy of the picture. (see step 4).
2. Measure and record tissue dimensions (length, width and thickness).
3. Identify the side that faced outward into the peritoneal cavity (marked with a surgical suture thread (X)) (Fig 1).

Fig 1:

[figure not shown]
4. Paint with ink (Indian ink) the side that was sutured against the abdominal wall and the surgical resection margins (Fig 2).

Fig 2:

5. Perform serial sectioning (10 sections of 0.3 cm) (the entire sample). For large samples (more than 3 cm width), include an additional cassette for each additional 1 cm of greatest dimension (Fig 3).

Fig 3:

[figure not shown]

6. Prepare blocks facing the side identified as A (Fig 4A, 4B).

Fig 4A:

Fig 4B:

7. Label the blocks with site number, patient code, M-Trap device code and the block number, from left to right: 1, 2, 3, 4...10.
  - a. Example: 03 01 A1, where 03 refers to the site number, 01 refers to the patient number, A refers to the M-Trap device code (\*see below) and 1 refers to the first block.
    - \* A: Right paracolic gutter
    - B: Left paracolic gutter
    - C: Liver segment (VI)
8. Fix the tissue in neutral buffered formalin for 16-24h at room temperature.
9. Process the tissue and embedded in paraffin following the department's pathology protocols.
10. Stain sections with Hematoxylin-Eosin.
11. Send the paraffin blocks, along with all photographs and the measurements of the tissue specimens, to the reference laboratory.

[name]/[name]  
Hospital Arnau de Vilanova, Anatomia Patològica  
[name]  
[name]

1. OVERVIEW

This statistical analysis plan (SAP) describes the planned statistical analyses of the data collected in the course of the clinical study of the M-Trap device.

This SAP provides additional details concerning the statistical analyses outlined in the protocol (version 3.0 dated 12 September 2017). The purpose of the SAP is to ensure the credibility of the study findings by pre-specifying the statistical approaches to the analysis of study data.

1.1. Study Objectives

The objective of this study is to assess the safety and the performance of the M-Trap device in the capture of metastatic tumor cells in Stage IIIC and IV ovarian cancer patients to support CE-marking of the device.

Safety objectives:

The primary objective is to demonstrate that the safety of M-Trap, as measured by freedom from device- and procedure-related major adverse events (MAE) through 6-months post-implantation, is non-inferior to historical controls.

The secondary objective is to collect long-term safety data to support device safety and post-market surveillance. Safety will be evaluated to demonstrate acceptable levels of device-related and procedure-related complications.

Performance objectives:

The primary objective is to confirm M-Trap performance, as determined by histological evidence of tumor cell capture.

The secondary objective is to assess disease focalization with use of the M-Trap device.

1.2. Study Design

This study is a prospective, multi-center, non-blinded, single arm study to evaluate the safety of the M-Trap device in Stage IIIC and IV ovarian cancer patients in comparison to historical controls in which up to 22 patients will be enrolled from up to 8 sites located in Spain.

Patients with one of the following outcomes after debulking surgery will be targeted in this study:

- Residual visible tumor ≤ 1 cm after primary debulking or
- Complete resection or residual visible tumor ≤ 1 cm after interval debulking surgery.

Up to twenty-two (22) patients will be treated in the clinical investigation to obtain twenty (20) evaluable patients.

Once patients have received the study treatment, they will be evaluated at 1 month, 3 months, 6 months, 9 months, 12 months, 15 months, and 18 months post-operatively.

This study will be conducted in a two-phase approach, as follows:

- (1) The first phase will enroll five (5) patients. Safety data at the 1-month time point will be collected, including physical examination, ultrasound, adverse events, and concomitant medications.
- (2) The second phase will enroll the remaining seventeen (17) patients and will commence upon approval by AEMPS to proceed with a continuation of the study.

	STATISTICAL ANALYSIS PLAN	MTRAP_SAP_v2.0_FINAL redacted.docx MTRAP Page 7/8
--	----------------------------------	--

1.3. Study Plan

1.3.1. Patient's Follow-up

Nine (9) visits are scheduled:

- Visit 0: Screening within 21 days
- Visit 1: Procedure (D0)
- Visit 2: 1 Month (± 1 week)
- Visit 3: 3 Months (± 2 weeks)
- Visit 4: 6 Months (± 2 weeks)
- Visit 5: 9 Months (± 1 month)
- Visit 6: 12 Months (± 1 month)
- Visit 7: 15 Months (± 1 month)
- Visit 8: 18 Months (± 1 month)

1.3.2. Study Device Use

The M-Trap Device (Metastatic Tumor Cell Trap Device) represents a breakthrough therapeutic strategy that provides a preferential site for the capture of disseminating tumor cells, transforming a systemic disease into a focalized disease where surgery, radiation, and chemotherapy have proven efficacy. M-Trap is an implantable surgical mesh comprised of a non-resorbable, polycarbonate polyurethane (PCPU) scaffold with a Type I collagen coating.

M-Trap is intended to be implanted into the peritoneal cavity during the tumor debulking procedure to capture disseminating tumor cells. Up to three (3) M-Trap devices will be surgically implanted via laparotomy in the right and left paracolic (pelvic) gutters and behind segment 6 of the liver within the peritoneal cavity of the patient at the time of surgical resection. Patients will receive standard platinum-based chemotherapy. If the cancer is diagnosed to have recurred, M-Trap devices with captured tumor cells will be removed via minimally invasive surgery (laparoscopy).

	STATISTICAL ANALYSIS PLAN	MTRAP_SAP_v2.0_FINAL redacted.docx
		MTRAP
		Page 8/9

1.3.3. Study Assessments

The following flowchart applies to the study:

Examination/ Assessment	Visit 0 Screening Within 21 days	Visit 1 Procedure (D0)	Visit 2 1M (±1W)	Visit 3 3M ¹ (±2W)	Visit 4 6M ² (±2W)	Visit 5 9M (±1M)	Visit 6 12M (±1M)	Visit 7 15M (±1M)	Visit 8 18M (±1M)
Signed Informed Consent	X								
Eligibility criteria check	X	X							
Demographics, medical history	X								
Physical examination	X	X	X	X	X	X	X	X	X
Biomarker CA-125	X			X	X	X	X	X	X
CT scan	X			X	X	X	X	X	X
Ultrasound		X	X	X	X	X	X	X	X
PCI ³	X	X							
Cytology/biopsy									X ⁴
Pathology (explant)									X ⁴
Adverse events	X	X	X	X	X	X	X	X	X
Concomitant medication	X	X	X	X	X	X	X	X	X

2. STATISTICAL METHODS

2.1. General Statistical Considerations

2.1.1. Time Points Definition

Baseline/Screening data is defined as the last available observation recorded before the first study device implantation for the patient.

Visit(n) data is defined as the last available observation on or before the Visit(n) time point following the first study device implantation for the patient.

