2.1.2. Handling Missing Data

In order to provide unbiased and informative findings, no replacement of missing values is planned for any parameters.

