2.1.3. Descriptive Statistics in Summary Tables

- Continuous variables will be summarized using standard quantitative statistics: number of non-missing observations, mean, standard deviation, median, quartiles and range (minimum and maximum observed values). The number of missing observations will also be specified.

¹ 3M visit must occur after the final chemotherapy infusion in interval debulking patients. The 3M CT scan will serve as the baseline for assessing disease progression for purposes of device removal.

² 6M visit must occur after the final chemotherapy infusion in primary debulking patients. The 6M CT scan will serve as the baseline for assessing disease progression for purposes of device removal.

³ Peritoneal Carcinomatosis Index.

⁴ To be performed at time of device removal. Device removal may occur earlier if conditions for device removal described in Section 6.2 of the protocol are met.

	STATISTICAL ANALYSIS PLAN	MTRAP_SAP_v2.0_FINAL redacted.docx
		MTRAP Page 9/10

- *Categorical variables* will be summarized using classical frequency statistics: number of non-missing observations and percentages by categories. Percentages will be calculated on the number of non-missing observations, and will be displayed using one decimal. The number of missing observations will also be specified.

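### SAP 2.1.1 defines visit data so that earlier values fill missed visits, against the SAP's own rule that missing values are not replaced

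*SAP*

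**What the plan says.** SAP 2.1.1 assigns follow-up data to visits with one sentence: "Visit(n) data is defined as the last available observation on or before the Visit(n) time point". The only lower limit is implantation. The windows in SAP 1.3.1 (±1 week at 1 month, ±2 weeks at 3 and 6 months, ±1 month from 9 to 18 months) are not mentioned, and *time point* is not defined.

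SAP 2.1.2, the next section, says that "no replacement of missing values is planned for any parameters". Protocol 10.3 takes the same position.

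SAP 2.1.3 adds, for summary tables, that "The number of missing observations will also be specified", and for categorical variables that "Percentages will be calculated on the number of non-missing observations, and will be displayed using one decimal".

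SAP 2.3.2 counts an assessment as a timing deviation only if it falls outside its window, so a visit late but in window is valid. SAP 2.4.4 lists what is tabulated at each visit from 1 to 18 months in the As-Treated population: physical examination, chemotherapy status, CA-125, CT, ultrasound and others.

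**The concern.** Taking the latest value up to a date, with no earliest date, is last observation carried forward. A programmer cannot apply it and also leave missing values missing, so two programmers could produce different tables from the same SAP.

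At stake is what the by-visit tables show. A carried value appears as a current one, N at later visits includes patients who have left the study, and the missing row understates what was not observed. By-visit N could also disagree with the attendance table required by SAP 2.4.1. One concrete case is the count of interval-debulking patients who have finished chemotherapy by the 3-month visit. If a patient has no 3-month record under the rule, her 1-month status would stand in for it.

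**Working it through.** **Inputs.** The windows are from SAP 1.3.1, the three rules from SAP 2.1.1 to 2.1.3, and the 20 evaluable patients from SAP 2.2. Assumptions that are not in the documents: a one-month window is 30 days, visits three months apart are 91 days apart, and the shares of late or missed visits are illustrative.

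**1. Carry-forward.** Take a patient last assessed at 6 months who dies at month 8. The latest post-implant observation not after month 9 is her 6-month value. The same search returns that value at 12, 15 and 18 months. SAP 2.1.2 would leave all four cells missing.

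**2. Missing counts.** Missing = 20 × share who miss the visit.
- 10%: 20 × 0.10 = 2 missing. The rule shows 0 wherever an earlier post-implant value exists.
- 20%: 20 × 0.20 = 4 missing. The rule again shows 0.

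Percentages are then taken over 20 instead of 18 or 16.

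**3. Late visits inside the window, if *time point* is the nominal date.** Observations left out of their own visit = 20 × share late.
- 25% late: 5. 50% late: 10. 75% late: 15.
- If dates were spread evenly over the window, the share would be 7/15 = 47% at 1 month, 14/29 = 48% at 3 and 6 months, and 30/61 = 49% from 9 months on. That is 9.3, 9.7 and 9.8 of 20.

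A late value left out of its own visit may reappear at the next one. At 18 months there is no next visit, so it is lost. CT and CA-125 are not scheduled at 1 month, so a 3-month result obtained after the nominal date has no earlier scheduled follow-up value to stand in for it. Visit 3 would be shown as missing although a valid result exists.

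**4. Age of a substituted value at the nominal date** = 91 days ± the previous visit's window.
- 6 and 9 months: 91 − 14 = 77 to 91 + 14 = 105 days.
- 12 months: 91 − 30 = 61 to 91 + 30 = 121 days.

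**5. Dependence on the undefined term.**

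| *Time point* read as | Carry-forward | Late in-window visits |
|---|---|---|
| Nominal date | Missed visits, visits after exit, missed assessments | Left out of their own visit |
| End of window | The same | Kept |
| Actual visit date | Assessments missed at an attended visit | Kept |

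The documents mostly use the term for a nominal month (SAP 2.1.5; the 18-month removal in Protocol 6.2.3). Protocol 6.2.3 also uses it once for a follow-up visit. Some carry-forward remains on every reading.

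**6. What does not move.** In SAP 2.5, the primary safety endpoint is event-based with its own 6 months ± 2 weeks, and tumour cell capture comes from the explanted devices. Recurrence comes from the reason for removal, and time to recurrence from the date of the visit at which removal is planned. None of these uses Visit(n) data. The sample size reproduces: with a null of 90% − 25% = 65%, requiring at least 17 successes in 20 gives an exact one-sided alpha of 0.044 and power of 0.867 at 90%. Both stay the same.

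**The case against.** The best defence is that this is loose wording and not a planned imputation. SAP 2.1.2 bars replacement for every parameter, the table layouts have rows or columns for missing values, SAP 2.4.1 reports who attended each visit and why patients left, and Listing 2 shows out-of-window visits. With about 20 patients, a misplaced value could be found by hand. This is fair as to intent, and a reader should not infer that the sponsor chose carry-forward as a method. But SAP 2.1.1 is the sentence that tells the programmer which value to use, and it says the opposite of 2.1.2.

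Three stronger inferences are tempting, and the documents do not support them.

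- *About half of valid visits are lost.* This needs the nominal-date reading and evenly scattered dates. The term is undefined and no visit dates are given. The footnote that the "3M visit must occur after the final chemotherapy infusion in interval debulking patients" does not show that visits run late, because no chemotherapy end date is stated.
- *The baseline CT for progression is shifted.* Progression for device removal is judged during the study under Protocol 6.2.3, and SAP 2.5 takes recurrence from the removal reason. SAP visit labels feed neither.
- *Every follow-up table is distorted.* Some items, such as new adverse events or medication changes since the last visit, make no sense when carried forward, and a programmer may well not apply the rule to them.

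**Conclusion.** The contradiction stands. As written, SAP 2.1.1 carries earlier post-implant values into missed visits and past death or withdrawal. This conflicts with SAP 2.1.2 and hides the missing counts required by 2.1.3. The displacement of late in-window visits is conditional: it follows on the nominal-date reading, which is the plain one, and its size depends on unknown visit dates.

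The effect is confined to descriptive by-visit follow-up tables, such as physical examination, CA-125, CT, and chemotherapy completion by the 3- and 6-month visits. It changes no primary result, power figure, time to recurrence or decision made during the study. It should be corrected before the tables are programmed, but it does not threaten the trial's main conclusions.

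**What to change.** Replace the Visit(n) sentence in SAP 2.1.1 with: *Visit(n) data is the observation recorded at the attended scheduled Visit(n) (if more than one, the closest to the target date); if the visit or assessment was not done, the value is missing and nothing is carried forward.* Keep visits outside the SAP 1.3.1 windows under their scheduled visit and flag them in Listing 2.

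This is better than setting everything outside the window to missing. A strict rule would drop a post-chemotherapy 3- or 6-month visit that ran more than two weeks late.

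The cost is one SAP sentence and a simple programming rule. N will be smaller at some visits, but it will be the true N and will agree with the attendance table.
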